6.1.8. Data Adjustments/Handling/Conventions

All collected data will be presented in listings. Data not subject to analysis according to this plan will not appear in any tables or graphs but will be included only in the data listings.

All *P* values will be displayed in four decimals and rounded using standard scientific notation (eg, 0.XXXX). If a *P* value less than 0.0001 occurs it will be shown in tables as < 0.0001.

Adverse events will be coded using the MedDRA version 24.0 thesaurus.

A treatment related AE is any AE with a relationship to the study drug assessed by the investigator. The investigator should carefully consider the list of possible manifestations of COVID-19 when assigning a relationship of specific AEs to the study drug.

For partial start dates:

- If the year is unknown, then do not impute the date but instead assign a missing value.
- If the year is known, but the month or month and day is unknown, then:
 - If the year matches the year of first dose date and the end date (if present) is after first dose date, or the AE/medication is ongoing, then impute as the month and day of the randomization date. If this produces a date after the end date, assign 01 January.
 - Otherwise, assign 01 January.
- If the year and month are known, but the day is unknown, then:
 - If the month and year match the month and year of the first dose date, then impute as the day of the randomization date. If this produces a date after the AE/medication end date, assign 01.
 - Otherwise, assign 01.

For partial end dates:

- If the year is unknown, then do not impute the date but assign as missing value.
- If the year is known but the month or month and day is unknown, then:
 - If the year matches the year of the last date of the study (date of last contact if subject lost to follow-up; date of completion or early termination otherwise), then impute as the month and day of the last date of the study.
 - Otherwise, assign 31 December.
- If the year and month are known, but day is unknown, then:
 - If the month and year match the month and year of the last date of the study, then impute as the day of the last date of the study.
 - Otherwise, assign the last day of the month.

In general, for quantitative laboratory values reported as ' $<X$ ' or ' $\leq X$ ', the lower limit of quantitation (LLOQ) will be used for analysis (i.e., the value of X will be used in the analysis for lab values reported as ' $<X$ ' or ' $\leq X$ '). Similarly, for quantitative laboratory values reported as ' $>X$ ' or ' $\geq X$ ', the upper limit of quantitation (ULOQ) will be used for analysis (i.e., the value of X will be used in the analysis for lab values reported as ' $>X$ ' or ' $\geq X$ ').

For analysis purposes, repeat laboratory test results will not be used unless the original laboratory value is missing or indicated as invalid, in which case the first non-missing repeated laboratory value will be used for data analysis.

7. Study Participants and Demographics

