### 10.1. Study Duration

The overall study duration is expected to be approximately 18 months (6 months of active enrollment and 2 months of follow-up in Part 1; 2 to 4 weeks for DSMB review of Part 1 results at Day 28 and selection of the Part 2 dose; 6 months of active enrollment in Part 2; and 2 months of follow-up in Part 2).

The sequence and approximate duration of the study periods will be as follows:

1. Screening: up to 72 hours
2. Treatment: 7 days
3. Follow-up: 28 days after randomization
4. Safety follow-up: 45 and 60 days after randomization

The maximum study duration for each participant is approximately 60 days.

The treatment duration for each participant is 7 days from the point of randomization (7 complete days of study drug administration after randomization). Screening/enrollment and baseline (Day 1) of the Treatment Period can take place on the same day if the required screening test results are available.

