#### 10.2.1 Screening

The participant should be screened within 1 day before enrollment in the study; screening and enrollment could occur on the same day. Procedures and local laboratory results collected within 72 hours of signed consent may be used for screening, although it is preferential to conduct screening activities within 24 hours, as long as they are collected within allowable study windows and meet all other study criteria.

The following procedures will be performed at screening:

- Obtain informed consent in writing

- Review inclusion/exclusion criteria
- Collect demographic information
- Record medical history, including current medications and therapies (e.g., prescription and nonprescription medications)
- Measure vital signs and SpO2 per institutional practice
- Measure weight and height
- 12-lead ECG
- Physical examination
- Neurological assessment
- Nasopharyngeal swab for virologic testing, if not collected within the previous 72 hours; NAAT confirmation of COVID-19 in a sample collected < 72 hours prior to randomization is required
- Collect blood and urine for the following tests (see [Section 10.3.3.1](#) for details on the components included in CBC, chemistry, coagulation, urinalysis and biomarker testing):
  - clinical laboratory tests including complete blood count (CBC), blood chemistry, coagulation tests, and urinalysis
  - sPLA2 enzyme activity
  - serum pregnancy test (participants of childbearing potential only)
  - biomarkers (cardiac troponin, CRP, and ferritin)
- Evaluate the participant using the WHO 9-point ordinal scale
- Record concomitant medications and concomitant therapies
- Assess and record any AEs occurring after informed consent was signed

Procedures for rescreening prospective participants who initially fail to meet study entry criteria are described in [Section 14.3](#).

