### 10.2.2 Treatment Period

The treatment period is defined as baseline (Day 1) through the completion of 7 days of study drug dosing which is expected on Day 7, but which may occur on calendar day 8, depending on the dosing regimen and timing of first dose of study drug.

#### 10.2.2.1 Day 1

Following completion of all assessments and confirmation of eligibility, the participant will be randomized via the IWRS. The following procedures will be performed on Day 1 of the Treatment Period:

- Measure vital signs and SpO2 per institutional practice

- Part 1 participants only: collect a PK blood sample prior to the first dose of IP (NOTE: Vital signs collection is not required prior to collection of PK blood samples, and daily vital signs may be collected before or after PK blood samples as local procedures allow.)
- Initiate IP dosing

After initiating treatment with the IP:

- Physical examination
- Part 1 participants only: collect a PK blood sample at the following times after the first dose: 30 minutes and 1, 2, 3, 4, 6, 8, and 12 hours
- Neurological assessment
- Evaluate the participant using the WHO 9-point ordinal scale
- Record concomitant medications and concomitant therapies
- Assess and record AEs

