### **11.2. Event Assessment and Follow-up of Adverse Events**

The occurrence of an AE or SAE may come to the attention of study personnel during hospitalization and at outpatient visits or via telephone.

All AEs will be captured on the appropriate case report form (CRF). Information to be collected includes event description, time of onset, clinician's assessment of severity, relationship to IP (assessed only by those with the training and authority to make a diagnosis), and time of resolution/stabilization of the event. All AEs occurring while on study must be documented appropriately regardless of relationship. All AEs will be followed to adequate resolution.

Site staff will record all reportable events with start dates occurring any time after informed consent is obtained through Day 60. At each study visit, the investigator will inquire about the occurrence of AE/SAEs since the last visit. Events will be followed for outcome information until resolution or stabilization.

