- For the time till all-cause mortality Cox proportional hazards model, time to all-cause mortality or censoring will be calculated as follows
 - If mortality occurs within 60 days post-randomization; then Time to all-cause mortality or censoring = date/time of death – date/time baseline + 1.
 - If mortality occurs on or after 60 days post-randomization; then Time to all-cause mortality or censoring = 60 days.
 - If mortality does not occur, and last follow-up is prior to 60 days; then Time to all-cause mortality or censoring = date/time of last follow-up – date/time baseline + 1.
 - If mortality does not occur, and last follow-up is on or after 60 days; then Time to all-cause mortality or censoring = 60 days.
- Change from baseline = value at current time point – value at baseline.
- TEAE = any adverse event with an onset or worsening date/time after the date/time of the first administration of IP and prior to the 30 days after last dose of IP.

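### SAP 6.1.8 matches a partial adverse event start date to the first dose but imputes the randomization date, so a possibly on-treatment event can be classed as not treatment-emergent

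*SAP*

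**What the plan says.** SAP 6.1.8 has one rule for partial start dates, shared by adverse events and medications. With the day unknown: "If the month and year match the month and year of the first dose date, then impute as the day of the randomization date". With the month unknown as well, it checks that the year is the first-dose year and that the event is ongoing or ended after first dose, "then impute as the month and day of the randomization date". The day-unknown branch has a safeguard: "If this produces a date after the AE/medication end date, assign 01". The month-unknown branch falls back to 1 January in the same way. No clock time is imputed.

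SAP 6.1.7 defines a treatment-emergent adverse event (TEAE) as one with onset or worsening "after the date/time of the first administration of IP and prior to the 30 days after last dose of IP". SAP 9.1 repeats this in similar terms.

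Protocol 10.2.2.1 sets the order on Day 1: "Following completion of all assessments and confirmation of eligibility, the participant will be randomized via the IWRS". Dosing is started after that. Protocol 8.1 allows consent, screening, randomization and dosing on one day.

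Protocol 11.2 has sites record events starting "any time after informed consent is obtained through Day 60". For the screening interval, Protocol 10.2.1 says "The participant should be screened within 1 day before enrollment in the study" and Protocol 10.1 gives "Screening: up to 72 hours".

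**The concern.** The rule tests the date against one anchor, first dose, and imputes another, randomization, which comes earlier. An event that may have begun on treatment can thereby be dated to before treatment. In the month-unknown branch this can happen just after the rule has confirmed that the event was ongoing or ended after first dose.

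This runs against the SAP's own approach. SAP 9.1 imputes a missing severity as Grade 3 and a missing relationship as related, on the stated ground of caution. A partial onset can get the opposite treatment.

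TEAE status decides what enters the overall, severe and related TEAE counts, the tables by system organ class and preferred term (SAP 9.1), and the table of TEAEs leading to drug withdrawal (SAP 9.1.1). Safety is part of the primary objective, and SAP section 10 leaves the Part 1 safety analysis as planned, so the rule governs the Part 1 tables.

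**Working it through.** The plan states no figure on this point, so the check is of date logic.

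Inputs: the day-unknown rule (SAP 6.1.8), the TEAE start condition (SAP 6.1.7), randomization before dosing (Protocol 10.2.2.1), and Part 1 allocation of 18 participants in a 5:5:5:3 ratio (SAP 3.2). The dates and times below are illustrative assumptions. The event's onset is known only to be in the first-dose month.

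| Randomization, first dose | Imputed onset | Dates only, strictly after | Dates only, on or after | Time set to 00:00 | Time set to randomization time | Time set to 23:59 |
|---|---|---|---|---|---|---|
| 10 Jan 10:00, 10 Jan 14:00 | 10 Jan | not TEAE | TEAE | not TEAE | not TEAE | TEAE |
| 10 Jan 22:00, 11 Jan 08:00 | 10 Jan | not TEAE | not TEAE | not TEAE | not TEAE | not TEAE |
| 31 Jan 23:00, 1 Feb 08:00 | 31 Feb | no such date | – | – | – | – |
| 28 Feb 23:00, 1 Mar 08:00 | 28 Mar | TEAE | TEAE | TEAE | TEAE | TEAE |

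- Earlier day, same month: not a TEAE under any of the five conventions.
- Same day: the result depends on a convention that the SAP does not state. The literal test, strictly after first dose, gives not TEAE unless a late time is assumed.
- Different months: the rule takes the day number of randomization and attaches it to the first-dose month. The result is an impossible date or one up to weeks after first dose.
- An onset dated only to a later month is set to the 1st of that month and stays after first dose, so it is not affected.

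Imputing the first-dose date and time would not be enough by itself. An onset equal to first dose still fails a strict test, so the boundary must also become at or after.

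Effect on one incidence, if all 18 were dosed as randomized: 1/5 = 20.0 points in a varespladib arm and 1/3 = 33.3 points in placebo. SAP 9.1 counts a participant once per preferred term. A preferred-term row therefore moves only if the participant has no other TEAE of that term, and the overall row only if the participant has no other TEAE at all.

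**The case against.** The strongest reply is that randomization and first dose are both Day 1 procedures and normally share a calendar date. A programmer comparing dates on an on-or-after basis would then get the sensible answer. That is fair as far as it goes. A reader might infer that every such event is read as not treatment-emergent, and the documents do not support that: it is certain only when randomization fell on an earlier day of the same month. For the same-day case the convention that rescues the rule is unwritten, and SAP 6.1.7 reads strictly.

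A reader might also infer from the calendar that the rule usually picks the less likely side. In a 30-day month with first dose on the 15th and consent 1 to 3 days earlier, 15 of 17 (88%) or 15 of 19 (79%) recordable dates fall after the dosing date. This treats a day-unknown onset as equally likely on every date. The documents do not support that, because adverse events are assessed daily through Day 21 and Protocol 11.2.3 asks for start date and time. Those facts also suggest that partial dates will be rare.

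There are backstops. All events are listed with those that are not treatment-emergent flagged (SAP 9.1), and serious events and deaths are reported without the TEAE limit (SAP 9.1.2). These limit the harm but do not correct the TEAE tables.

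Lastly, the end of the TEAE window differs between texts. Protocol 11.1.4 runs to the end of the reporting period, Day 60 by Protocol 11.2. Protocol 13.1.5.1 and SAP 6.1.7 and 9.1 stop before 30 days after last dose. With last dose on Day 7, the difference is Days 37 to 60 (7 + 30 = 37; 60 − 37 + 1 = 24 days). One might infer that the tables are ambiguous. They are not: the analysis texts agree, and Protocol 13.1 leaves the final analyses to the SAP. This is editorial only.

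**Conclusion.** The mismatch in SAP 6.1.8 is real and should be corrected. It classes a possibly on-treatment event as not treatment-emergent when randomization was on an earlier day of the first-dose month, leaves the usual same-day case undetermined, and can fail outright when the two dates fall in different months.

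The effect is probably on few events, mainly non-serious ones. The documents do not allow the number to be derived. The shift of 20.0 or 33.3 points is what one participant can do to one Part 1 row under the conditions shown, not an expected bias.

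**What to change.** Before the Part 1 database lock:

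- In SAP 6.1.8, separate adverse events from medications. For adverse events meeting the existing match conditions, impute the first-dose date and time. Keep the end-date fallback, and leave the medication rule unchanged.
- In SAP 6.1.7 and 9.1, treat onset at or after first dose as treatment-emergent unless the known date parts or the end date show an earlier start.
- As an editorial matter, align the end of the window in Protocol 11.1.4 with the 30-day rule in Protocol 13.1.5.1 and SAP 6.1.7 and 9.1.

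The cost is a few sentences and a separate partial-start rule in the programs, with no new data. The downside is that a few pre-dose events with partial dates may be counted as TEAEs. That is bounded by the short interval from consent to dosing, since events are recorded only from consent and screening lasts at most 72 hours.

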### **9.5. Discontinuation of Study Intervention**

#### **9.5.1 Individual Participant Halting Criteria**

If a clinically significant finding is identified (including, but not limited to, deterioration from baseline) after enrollment, the investigator or qualified designee will determine if any change in participant management is needed. Every effort should be made to administer the planned doses. Dosing should be held for a participant who experiences any of the following toxicities:

- Any Grade  $\geq 2$  creatinine increase ( $> 1.5 \times$  baseline or ULN)
- Any new, treatment-emergent occurrence of any of the following adverse events of special interest:

- Cerebrovascular accident
- Acute coronary syndrome
- Supraventricular arrhythmia requiring urgent medical intervention
- Any ventricular tachycardia/fibrillation including Torsade de Pointes
- Hepatic toxicity with AST and/or ALT  $\geq 3 \times$  ULN for 2 days or  $> 5 \times$  ULN on one occasion

If a participant becomes unable to swallow the IP due to worsening of their condition, nasogastric administration or a dose delay may be considered in consultation with the medical monitor. In general, treatment with IP should continue for the full 7 days unless the participant is unable to continue treatment or if it is the participant's best interest to discontinue treatment. If a participant must discontinue IP, every effort will be made to continue the participant in the study through Day 60. If a participant experiences an SAE judged to be related to the IP, the treatment for that participant will be permanently discontinued from the IP, but every effort will be made to continue the participant in the study through Day 60.

Any new clinically relevant adverse finding will be reported as an adverse event (AE) as defined in [Section 11.1](#).

Discontinuation from IP does not mean discontinuation from the study, and remaining study procedures should be completed as indicated by the study protocol.

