### **13.1.5.2 Clinical Laboratory Evaluations, Vital Signs, Electrocardiograms, and Pulse Oximetry**

Summary statistics of clinical laboratory measures will be presented by treatment group for each assessment. The number and percentage of participants with at least 1 post-baseline potentially clinically significant abnormality will be presented by treatment group for selected parameters.

The same approach will be used for vital signs, ECGs, and pulse oximetry.

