6.1.5. Analysis Visit Windows

Visits will be analyzed as scheduled. The windows follow the Schedule of Events in the Protocol. Screening, enrollment, and Day 1 of the Treatment Period can take place on the same day if the required screening test results are available.

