9.2. Clinical Laboratory Evaluations

Laboratory test results for chemistry, coagulation, hematology and urinalysis will be summarized descriptively by treatment and visit as both observed values and change from baseline values.

The number and percentage of participants with at least 1 post-baseline potentially clinically significant abnormality will be presented by treatment group for selected parameters. The number of participants with clinical laboratory values below, within, or above the normal range by visit and in relation to baseline will be tabulated for each clinical laboratory analyte by treatment group (shift table).

Individual data listings of laboratory results will be presented for each subject. Flags will be displayed for values outside of the laboratory's normal reference limits.

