9.4. Vital Signs and Pulse Oximetry

Descriptive summaries of actual values and changes from baseline will be calculated systolic blood pressure, diastolic blood pressure, heart rate, respiratory rate, body temperature, and SpO₂.

The number and percentage of participants with at least 1 post-baseline potentially clinically significant abnormality will be presented by treatment group for selected parameters.

Individual data listings of vital signs (observed and change from baseline) will be presented for each subject.

9.5. 12-Lead Electrocardiogram

Descriptive summaries of observed values and changes from baseline will be calculated for heart rate, PR interval, QRS interval, QT interval and QTcF by visit and treatment group.

Frequencies and percentages of investigator interpretation of ECG results (normal, abnormal clinically significant, and abnormal not clinically significant) will be presented by visit and treatment group.

The safety ECG data will be provided in a listing.

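### The SAP's no-repeats rule for laboratory values has no exception for the ever-abnormal count in SAP 9.2, and SAP 9.5 omits, undeclared, the ECG count that the protocol specifies

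*SAP*

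**What the plan says.** **Laboratory values.** For analysis, SAP 6.1.8 provides that "repeat laboratory test results will not be used unless the original laboratory value is missing or indicated as invalid". Where that exception applies, the earliest available repeat takes the original's place. The same section keeps everything visible at participant level: "All collected data will be presented in listings". SAP 6.1.5 adds only that "Visits will be analyzed as scheduled". The SAP gives no definition of a repeat and no rule for samples drawn outside the scheduled visits. SAP 9.2 then plans by-visit summaries, shift tables, and a count of participants with "at least 1 post-baseline potentially clinically significant abnormality" for selected parameters.

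**Dose-hold limits.** Protocol 9.5.1 lists a creatinine limit and an item beginning "Hepatic toxicity with AST and/or ALT". The AST/ALT item has two limbs: at least 3 x ULN for two days, or above 5 x ULN once. The rhythm criteria in that section are clinical events. None is an ECG interval value.

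**ECG.** After describing the participant-level abnormality count for laboratory tests, Protocol 13.1.5.2 says: "The same approach will be used for vital signs, ECGs, and pulse oximetry". Protocol 13.1.5 says the same. SAP 9.4 carries the count over for vital signs and SpO2. SAP 9.5 does not carry it over for ECG. It says that descriptive summaries "will be calculated for heart rate, PR interval, QRS interval, QT interval and QTcF by visit and treatment group", and adds investigator interpretation categories by visit. SAP section 10 states that the planned safety analyses for Part 1 are unchanged.

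**The concern.** Keeping one value per visit is sensible for a mean or a shift table. An ever-abnormal count asks a different question: did this participant cross the limit at any time after baseline? A rule that discards valid values can only lower that count.

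The protocol describes liver enzyme rises with this drug as modest and transient, so a peak can fall between scheduled draws or appear in a follow-up sample. Safety is part of the primary objective. After the recruitment pause, Part 1 is to be reported unblinded with 18 participants, so each participant weighs heavily in any safety percentage.

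The ECG gap is a separate matter. A table that the protocol promises is absent from the SAP, and the section that records changes does not mention it. Summaries by visit, whether of intervals or of investigator interpretation, do not show how many participants were abnormal at least once.

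**Working it through.** The documents state no figure to reproduce. The check compares the texts and counts from the protocol's schedule.

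**1. Which value feeds the SAP 9.2 count under SAP 6.1.8**

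- Original valid and abnormal, repeat normal: the participant is counted, because the original is kept.
- Original valid and not abnormal, repeat valid and abnormal: the repeat is not counted. The participant is missed unless another retained value qualifies.
- Original missing or invalid: the first non-missing repeat is used.
- Extra draw on a non-visit day: undetermined. It could be a repeat, or an unscheduled sample for which no rule exists.

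The loss is therefore confined to the second case and, depending on how a repeat is defined, the fourth.

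**2. What scheduled draws can show**

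Protocol 10.2.2.4, 10.2.2.7, 10.2.3.2 and 10.2.3.5 place post-baseline laboratory draws on Days 4, 7, 14 (window 2 days either way) and 28 (window 2 days either way).

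- Draws within the seven treatment days: Days 4 and 7, so 2 of 7.
- Nominal gaps: 7 − 4 = 3; 14 − 7 = 7; 28 − 14 = 14 days.
- Shortest gaps with windows: 12 − 7 = 5 and 26 − 16 = 10 days. The overall minimum stays at 3.

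No two scheduled draws are consecutive. This assumes draws are made on schedule; a rescheduled or early-termination visit could fall elsewhere. If the two-day limb means consecutive days, it needs an extra sample. If two separate days suffice, Days 4 and 7 could show it. The limb above 5 x ULN needs one value, and so can the creatinine limit. A scheduled original can supply either, and the rule keeps it.

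**3. Size**

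- One missed participant in a Part 1 active arm: 1/5 = 20 percentage points.
- One in a planned Part 2 arm of 36: 1/36 = 2.8 points. This is hypothetical, since one Part 2 participant had been recruited at the pause.

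The number missed depends on the share q of participants whose only qualifying value is an excluded repeat. The documents do not give q. As an assumption only, with n = 18 in Part 1:

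- q = 1%: expected 18 × 0.01 = 0.18; chance of at least one 1 − 0.99^18 = 17%.
- q = 10%: expected 18 × 0.10 = 1.8; chance of at least one 1 − 0.90^18 = 85%.

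The range is too wide to be an estimate. It shows only that the answer depends on q.

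**4. Participant-level abnormality count, protocol against SAP**

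| Domain | Protocol 13.1.5 and 13.1.5.2 | SAP |
|---|---|---|
| Laboratory | specified | kept (9.2) |
| Vital signs | specified | kept (9.4) |
| Pulse oximetry | specified | kept (9.4) |
| ECG | specified | absent (9.5) |

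SAP section 10 lists changes to efficacy reporting and states that Part 1 safety analyses are unchanged. The ECG omission is not among the declared changes.

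**The case against.** **Repeats are not lost.** They are used when the original is missing or invalid, all values are listed, and SAP 9.2 flags out-of-range results in the listings. With Part 1 arms of 5 or 3, a reader can find an individual peak there. This stands, so it would be wrong to infer that repeats are barred from every analysis. A listing is still not the count.

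**Repeats may run lower.** A first value repeated because it was extreme will often be followed by a lower one, and the rule keeps the extreme original. This stands too: the documents do not show that repeats tend to carry the peak. Information is lost only when the repeat is higher or is the only qualifying value.

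**Adverse event reporting is a backstop.** Protocol 9.5.1 and 10.3.3.1.2 require clinically relevant findings to be reported as adverse events. SAP 9.1 tabulates by maximum grade, and SAP 9.1.1 tabulates events leading to drug withdrawal. This is a partial answer. Reporting depends on the investigator's judgement. Protocol 11.1.1 does not treat COVID-19 worsening as automatically an adverse event, and Protocol 9.5.2 names kidney and liver injury as complications of the disease. The SAP specifies no table of temporary interruptions.

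**A reader might infer that the tables must miss the peaks that stop dosing.** The documents do not support this. A single scheduled original can meet the creatinine limit or the higher AST/ALT limb. An extra draw the day after a scheduled one may be an unscheduled sample and not a repeat.

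**A reader might try to size the effect from the schedule.** If onset is assumed uniform over Days 2 to 8, rises of 1, 2 and 3 days miss every scheduled draw in 5/7 (71%), 3/7 (43%) and 1/7 (14%) of cases. Those figures describe the visit schedule. They do not measure the repeat rule, and a rise that nobody sampled cannot be recovered by any rule.

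**ECG.** A reader might link the missing count to dose holding. No hold criterion is an ECG interval, and the protocol reports no evidence of a QT effect in earlier studies. The protocol also promises the count only for selected parameters, so it does not commit to any particular QTcF threshold.

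**Conclusion.** Two defects hold on the text.

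First, SAP 6.1.8 excludes a valid repeat that exceeds a valid original from the SAP 9.2 ever-abnormal count, and the SAP leaves repeats undefined and unscheduled draws unaddressed. The direction is known: the count can only be too low. The size is not. It depends on how often an excluded value is a participant's only qualifying one, and on cut-offs for a potentially clinically significant value that the SAP does not list. For the same reason, the match between that table and the limits in Protocol 9.5.1 cannot be checked. One missed participant would be 20 percentage points in a Part 1 active arm. The point about the two-day AST/ALT limb rests on reading it as consecutive days.

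Second, and independently, SAP 9.5 omits an ECG count that the protocol specifies, without declaring it. This needs no assumption.

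Neither defect removes safety data from the report, since listings remain and adverse event tables give partial cover. Both affect specified summary tables and should be corrected before those tables are produced.

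**What to change.** - **SAP 6.1.8:** limit the no-repeats rule to by-visit summaries, and define a repeat as distinct from an unscheduled sample.
- **SAP 9.2:** base the ever-abnormal laboratory count on all valid recorded post-baseline values: scheduled, unscheduled and repeat. Show the number of draws per arm beside it.
- **SAP 9.4:** state the same all-values basis for the vital-sign and SpO2 counts.
- **SAP 9.5:** restore the participant-level ECG abnormality count for selected parameters, as the protocol specifies, or declare its removal in section 10.

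The cost is a few SAP sentences, one ECG table and a little programming. It relies on values that reach the database; the documents do not show whether every extra draw is recorded. Participants sampled more often have more chances to show an abnormality, so an all-values count can differ between arms because of testing frequency alone. Showing the number of draws makes that visible but does not remove it.
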